# **RESEARCH METHODS/PLANS**

Design: Cross-sectional, repeated-measures design.

*Participants:* We will recruit children aged between 7 and 16 years old with a diagnosis of hemiplegia (due to CP or stroke) at Gross Motor Function Classification System (GMFCS) Levels I-III and Manual Ability Classification System (MACS) Levels I-II. We will also recruit a comparison group of age and gender-matched typically developing peers. Inclusion criteria include the ability to read and write English. Children need to be able to see, hear and respond to auditory and visual cues. As such, exclusion criteria are a greater than 10-degree elbow or shoulder flexion contracture in the affected arm, uncorrected visual deficits (e.g., homonymous hemianopsia, oculomotor disturbance, or cortical visual impairment), uncontrolled photosensitive seizures (occurrence of at least one seizure in the last 3 months), hemineglect or cognitive impairments that would prohibit participation (as judged by a parent).

**Recruitment and sites:** The research assistant (RA) will consult the child's electronic medical records and the clinic MD to determine eligibility. They will approach eligible children and families and provide an overview of the study. Children and caregivers will complete informed assent and consent. Recruitment and data collection will take place at Maine Medical Center Pediatric CP clinic (Portland, ME), Spaulding Salem Outpatient Center for Children CP clinic (Salem, MA), and Massachusetts General Hospital Pediatric Stroke clinic (Boston, MA). In addition, we will email the families of the 62 children with CP or stroke in our lab database to invite them to participate in the lab. Typically developing children recruited via emails from our database will also be tested in the ReGame-VR Lab.

**Sample size and power**: We will recruit a convenience sample of 40 children with hemiplegia and 40 typically developing children. This pilot study is designed to obtain estimates of within- and between-child variability for effect size calculations to power a subsequent, more rigorous study design.

*Institutional Research Board Approval:* IRB approval will be obtained from Northeastern University, facilitating a shared and expedited agreement with IRBs of participating sites.

[figure not shown]

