### **Study Procedures**

## Outcome measures

Aim 1: Feasibility will be determined by achievement of the following:

- a. Recruitment of 40 children with hemiplegia in 24 data collection visits at study sites (average 2/visit: 3 sites, 2 visits/month, 4 months);
- <5% of participants reporting adverse effects (dizziness or motion sickness) during or within 15 minutes post HMD-VR use; and
- c. 90% of participants able to complete the whole protocol in the available clinic timeframe.

**Aim 2:** *2.a.Paper-and-pencil test:* Total score from the Beery-Buktenica VMI test 6th Edition Short form. *2.b. Touchscreen computer and HMD-VR:* Eye-hand proximity, defined as the lag between eye end time and hand end time (i.e. eye movement time – hand movement time), is a gold-standard measure of visual-motor integration that quantifies the coordination of eye and hand movements.

**Aim 3:** Total movement time during the visual-motor integration object transport task in HMD-VR with and without the complex environment.

**Secondary outcomes**. Multiple other temporal and spatial variables related to eye, head and hand movements will be collected for hypothesis-generating purposes. These include reaction time, movement time, amplitude (eye and hand), touch and transport accuracy (hand), peak velocity, sub-movements and trajectory straightness (hand), and spatial position and pitch, yaw and roll orientations.

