Data management and analysis: We will follow established procedures for eve tracking and kinematic data processing to discard trials in which artifacts are present or children are looking elsewhere and to determine head and hand movement start and end times. RStudio will be used for data analyses. We will check assumptions of normality for parametric analyses; if un-met, non-parametric equivalent tests will be undertaken. Aim 1: Feasibility outcomes will be recorded with counts and proportions. Aim 2: We will calculate the median of the 5 trials for each hand and target location. Of primary interest are estimates of variability as inputs needed for sample size calculations for the subsequent study. Recognizing lack of power, we will undertake inferential statistics for hypothesis generating purposes, including a multiple correlation using Pearson's t-test for each hand and target location. Aim 3: Paired t-tests per hand. Hypothesis-generating analyses for secondary outcomes will compare performance estimates within individuals (touch screen vs HMD-VR, dominant vs non-dominant hand) and between individuals (CP vs typically developing), accounting for age, lesion, and HMD-VR experience. Equipment related: 1) Sanitization: We use Cleanbox VR technology to disinfect VR headsets using UVC light. All peripherals will be sanitized with alcohol wipes and left to dry for a minimum of 15 minutes between users. 2) Transport/set up: Potential difficulties transporting and setting up equipment in different settings can be mitigated by diligent equipment protection. We have transported equipment many times for other studies at the Boston Children's Museum. HMD-VR tracking accuracy is not affected by differing ambient light levels. Study related: 1) Reliability of VMI scoring: The PI (a pediatric physical therapist) will train for VMI scoring by using the VMI manual, attending a web-based presentation on scoring, and scoring practice tests. 2) Lack of experience with eye-tracking processing/analyses: We will consult with [name], Assistant Professor in the College of Science at Northeastern and eye-tracking expert, who will advise on analyses. [name] was unable to be a named investigator on this grant due to budget restrictions. 3) Recruitment: Previous recruitment at Boston Children's Hospital CP clinic (unfortunately not a site for this study due to lack of space for clinic VR assessments) yields 2-3 eligible participants/week for identical inclusion criteria. Estimates from other sites are between 3-10 eligible children per clinic. 4) Time for in-clinic assessment: Recognizing the many demands on children and families' time in a busy clinic

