
environment, we will endeavor to approach families at their arrival and leverage positive relationships with clinic staff to determine the optimal testing time.

Participant related: 1) Previous experience with VR: This may impact performance; this information will be collected in the demographic questionnaire and included as a covariate in the analyses. 2) Potential impact of HMD weight on head or reaching movements: There are no studies of impact of HMD weight on children's movements; the short duration of our testing should mitigate any issue. 3) Left vs right-sided lesion differences in spatial abilities: We will include hemispheric lesion side as a covariate in the analyses, but this is complicated by the fact that many children with unilateral impairments have bilateral lesions. Any hemispheric-specific differences will inform the next study. 4) Intra- and inter-individual variability in this population: Children with hemiplegia are a heterogeneous population and their performance varies across repeated tests within individuals and between children. We will take this into account by basing sample size calculations for subsequent work on effect sizes from this study.

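### The readable text does not state the order of the within-child conditions, and the Aim 3 paired t-test has no order term, so a fixed order would mix practice or fatigue into the environment effect

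*Combined protocol and SAP*

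**What the plan says.** The Design line reads "Design: Cross-sectional, repeated-measures design". Under Outcome measures, the Aim 3 outcome is "Total movement time during the visual-motor integration object transport task in HMD-VR with and without the complex environment". Under Data management and analysis, the entire Aim 3 method is "Aim 3: Paired t-tests per hand".

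The same paragraph plans hypothesis-generating analyses of secondary outcomes that will "compare performance estimates within individuals (touch screen vs HMD-VR, dominant vs non-dominant hand" and also compare the two groups. The adjustment variables named there are age, lesion and VR experience. Order is not among them.

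Under Participant related, the plan notes "Previous experience with VR: This may impact performance" and deals with it by a questionnaire item used as a covariate. The same list accepts that performance varies when a child is retested, and answers this by basing later sample sizes on effect sizes from this study.

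On size and purpose, Sample size and power states: "We will recruit a convenience sample of 40 children with hemiplegia and 40 typically developing children". It adds: "This pilot study is designed to obtain estimates of within- and between-child variability for effect size calculations".

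The readable text contains no statement on sequence, randomised or counterbalanced order, practice trials or a period term. The Study Procedures heading is followed at once by Outcome measures. The tasks, the target locations, the complex environment and the flow of a session are not described in the text available. The opening part of the document and a figure were not available either.

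**The concern.** A paired t-test on two conditions attributes the whole mean within-child difference to the condition. If every child meets the conditions in the same order, that difference is the environment effect plus whatever changes between the first and second block. Children new to a headset may speed up with practice, and children with hemiplegia may slow with fatigue. With the simple scene (no complex environment) first, practice would hide a true slowing and fatigue would imitate one. With the complex scene first, the signs reverse. Recruiting more children tightens the estimate around the wrong value.

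The VR-experience covariate does not address this. It is a single value per child, so its main effect cancels from a within-child difference. It could only explain why the difference varies between children, and the plan offers it for previous experience, not as a control for order.

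At stake is the mean Aim 3 contrast and any standardised effect built on it, which this pilot is meant to pass to the next study.

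**Working it through.** **No figure to reproduce.** The documents give no alpha, SD, expected effect or power for Aim 3. The calculations below show what order would do under stated assumptions.

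**Inputs**
- From the document: 40 children per group. The plan does not say whether the groups are analysed separately or together; one group, n = 40 pairs, is assumed.
- Assumed: two-sided alpha 0.05, and no true environment effect when computing false-positive rates.
- Assumed: a first-to-second block shift, written either as a multiple d of the SD of the paired difference or as a percentage of mean movement time.

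**1. Fixed order, plain paired t-test.** The test statistic is noncentral t with 39 degrees of freedom and noncentrality d × √40.

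| d | Noncentrality | Rejection rate |
|---|---|---|
| 0.1 | 0.63 | 0.095 |
| 0.2 | 1.26 | 0.235 |
| 0.3 | 1.90 | 0.457 |
| 0.5 | 3.16 | 0.869 |

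For scale, 40 pairs have 80% power at d of about 0.45.

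**2. The same in percentage terms.** Noncentrality = practice % ÷ (SD % ÷ √40), with √40 = 6.32.
- SD 20%, practice 5%: 5 ÷ 3.16 = 1.58, rejection rate 0.338.
- SD 20%, practice 10%: 10 ÷ 3.16 = 3.16, rejection rate 0.869.
- Extremes over SD 15% to 30%: 0.177 (practice 5%, SD 30%) to 0.984 (practice 10%, SD 15%).

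**3. Effect size carried forward.** Assume a true slowing of 10%, SD 20% and practice of 5%. Pairs are those needed for 80% power.

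| Order | Apparent effect | Effect ÷ SD | Pairs |
|---|---|---|---|
| No order effect | 10% | 0.50 | 34 |
| Simple always first | 10 − 5 = 5% | 0.25 | 128 |
| Complex always first | 10 + 5 = 15% | 0.75 | 16 |

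The planned size of the next study could therefore err in either direction. With fatigue in place of practice, the last two rows change places.

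**4. Balanced order (20 children in each order).** The shift is +d in one half and −d in the other, so it cancels from the mean and the estimate is unbiased. In the plain test it remains in the variance: the expected squared SD rises by the factor 1 + d² × 40/39. At d = 0.5 this is 1 + 0.25 × 1.026 = 1.256, so the SD is about 12% too large. Simulated false-positive rates (200,000 replicates):

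| d | Plain paired t | With order term |
|---|---|---|
| 0 | 0.050 | 0.050 |
| 0.2 | 0.045 | 0.049 |
| 0.3 | 0.040 | 0.050 |
| 0.5 | 0.029 | 0.050 |

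Balance therefore removes the bias, and the order term restores the nominal error rate.

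**The case against.** The strongest objection is that the order rule may exist. A procedures heading with no procedures under it, a missing figure, and analyses that refer to trials and targets described nowhere in the readable text all suggest that the testing sequence is set out somewhere not seen. This stands. A reader might infer that the plan has no counterbalancing and that its contrasts are confounded, but the documents do not support that. Confounding needs a fixed or unbalanced order, and none is stated. That all testing happens in one sitting is a fair inference from the feasibility target of finishing within the clinic timeframe, but it is not stated outright.

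Second, a paired t-test is not an error in itself. With balanced order it is unbiased and only conservative. This also stands, and it makes the order term a refinement in that case.

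Third, the plan's main product is variability. An order shift common to all children under a fixed order leaves the SD of the paired differences and the Aim 2 correlations unchanged, and only the mean contrast moves. This is correct and limits the point. It does not remove it, because Participant related says that effect sizes from this study will set later sample sizes. The touchscreen-versus-headset comparison is explicitly hypothesis-generating. Aim 3 does not carry that label itself; the remark about lack of power is attached to Aim 2.

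Fourth, balancing everything has a price. Environment, device and starting hand give 2 × 2 × 2 = 8 sequences, or 40 ÷ 8 = 5 children per sequence per group, and mixed device and hand orders add order variance to the Aim 2 correlations. This stands and narrows the fix to environment order.

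The missing material does not explain away the absence of an order term. The analysis paragraph is readable and gives the Aim 3 method in full.

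**Conclusion.** The point holds as a conditional one. The readable text leaves the order of conditions unstated, and the stated Aim 3 analysis has no order or period term. If the order is fixed or unbalanced, the environment contrast and the effect size passed on include practice or fatigue, with unknown sign, and a larger sample does not help. If the order is balanced, the plain test is valid but conservative, with an error rate of about 0.029 against 0.050 at an order effect of 0.5 SD.

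The fixed-order rejection rates (0.095 to 0.869 for shifts of 0.1 to 0.5 SD, or 18% to 98% over the percentage scenarios) illustrate size only. They rest on assumed SDs, practice effects and alpha, on 40 pairs and on a fixed order that no text states. They should not be read as the error rate of this study. The change is worth making because it is cheap and useful in both cases.

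**What to change.** 1. State in the procedures the order in which each child meets the two environments. If a balanced order already exists, a sentence saying so is enough.
2. If it does not, allocate each child from a prepared list to simple-complex or complex-simple, in equal numbers within each group (20 and 20), and record the order actually used.
3. For Aim 3, replace the plain paired t-test per hand with the order-adjusted paired contrast. This is the mean of the two order-specific mean differences, tested with their pooled within-order SD on 38 degrees of freedom per group. A mixed model with environment and period is the equivalent.
4. Report the period effect as an estimate of within-session learning or fatigue. Pass the order-adjusted SD to the next study, since the unadjusted one is inflated under a balanced order.
5. Treat balancing of device order and starting hand as optional. Those contrasts are hypothesis-generating, and balancing them adds order variance to the Aim 2 correlations. Whatever is chosen, state and record it.

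The cost is one degree of freedom, a list that staff must follow, and no added testing time. The adjustment does not remove unequal carry-over, where the effect of going first differs between the two conditions. That limitation should be stated with the results.
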